### **6.2.2. Secondary Analyses**

#### *Adjusted estimates*

We will perform analyses aimed at obtaining estimates of treatment effectiveness, adjusting for any imbalances in baseline subject characteristics between groups. The objectives of these analyses are to estimate the influence of covariates on the outcome and to use them to improve the estimated difference between treatment groups. Logistic regression models will be used to identify and estimate the effect of multiple prognostic factors on the probability of SSI and other categorical outcomes.

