## **6. Data Analysis**

### **6.1. Sample Size and Power**

#### **6.1.1. Primary Aim – Effectiveness**

The total sample size for the trial is estimated based on the primary outcome. We then estimate, on the basis of the sample size for the primary aim, the power we will have to detect clinically significant differences in the secondary aims. All sample size and power estimates are based on two-tailed tests, enabling us to detect an increase or decrease in rates of outcomes with use of prophylactic NPWT.

The baseline rate of SSIs in obese women from our preliminary data is 11.6%. Furthermore, rates of SSIs at the study sites in all women range from 6 to 12% and are expected to be higher in obese women. Assuming a conservative baseline rate of 10%, we estimate that a total of **2850** subjects (1425 NPWT and 1425 standard care) will be sufficient to detect a 30% relative difference in SSIs, with 80% power and 5% significance level and

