**Table 4: Sample size estimation**  
(Power=80%, 2-tailed,  $\alpha =0.05$ )

Detectable relative difference	Anticipated SSI rate with NPWT (assuming 10% baseline rate)	Sample size (assuming 5% loss to follow-up)
50%	5.0%	910
40%	6.0%	1514
33%	6.7%	2316
30%	7.0%	2850
25%	7.5%	4215
20%	8.0%	6760

accommodation of 5% loss to follow-up (Table 4). This 30% difference represents the difference between a 10% rate of SSI in the standard care group and a 7% rate in the NPWT group.

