## **6.2. Data Analysis Plan**

### **6.2.1. Primary Analyses**

Data analyses will adhere closely to the CONSORT guidelines. Analyses will follow the intention-to-treat principle in which subjects will be analyzed in the group to which they were randomized, regardless of whether or not they received the assigned intervention.

Descriptive statistics will characterize the group of individuals recruited and investigate comparability of the two groups at baseline. Formal statistical testing will be limited to selected baseline characteristics considered to be prognostic factors for the primary outcome such as emergent cesarean, type of skin incision, and prolonged rupture of membranes. The categorical prognostic factors will be compared between trial groups by using the Chi-squared or Fisher's exact tests as appropriate. The two-group independent t-test and Mann-Whitney U test will be used to compare normal and non-normally distributed continuous variables, respectively. The primary outcome and other categorical secondary outcomes will be compared between intervention groups by using the Cochran-Mantel-Haenszel test. We will calculate common relative risks and 95% confidence intervals associated with the primary and secondary outcomes.

We will use the Breslow-Day test to assess homogeneity of the effect across subgroups (study sites, BMI category [30 – 39.9,  $\geq 40$ ], and scheduled/non-labor or unscheduled/labor cesareans, skin incision type [low transverse, high transverse, midline vertical], diabetes status). We will also conduct time-to-event analyses by using Kaplan Meier and Cox regression models to examine the pattern of SSIs in the two groups.

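### The plan reports relative risks, but its adjusted estimates default to a conditional odds ratio and its homogeneity test takes equal odds ratios as its null (minor, secondary analyses only)

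*Combined protocol and SAP*

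**What the plan says.** The design is framed on the relative scale. Section 6.1.1 states that 2850 "subjects (1425 NPWT and 1425 standard care) will be sufficient to detect a 30% relative difference in SSIs", and the text with Table 4 explains this as the "difference between a 10% rate of SSI in the standard care group and a 7% rate in the NPWT group".

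Section 6.2.1 (Primary Analyses) compares categorical outcomes by the Cochran-Mantel-Haenszel test and then fixes the measure: "We will calculate common relative risks and 95% confidence intervals associated with the primary and secondary outcomes". The same section continues: "We will use the Breslow-Day test to assess homogeneity of the effect across subgroups". The subgroup factors are site, BMI category, scheduled or unscheduled cesarean, skin incision type and diabetes status.

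Section 6.2.2 (Adjusted estimates) plans estimates of treatment effectiveness that allow for baseline imbalance, and intends covariates to sharpen the contrast between arms. The only model it names is in this sentence: "Logistic regression models will be used to identify and estimate the effect of multiple prognostic factors on the probability of SSI". The sentence goes on to cover other categorical outcomes.

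The document never names the odds ratio as a measure. It does not state the scale of the adjusted treatment effect, plan a conversion to an RR, or state the scale on which homogeneity is judged.

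**The concern.** The treatment coefficient of a logistic model is a conditional log odds ratio. It differs from the RR in two ways. The odds scale lies further from 1 than the risk scale. Odds ratios are also non-collapsible, so conditioning on prognostic covariates moves them further from 1 even when the arms are perfectly balanced. An adjusted OR printed beside the trial's common RR can then be read as covariates having strengthened the effect, when only the measure has changed. For the safety aim, the same shift makes a harm look larger.

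The homogeneity test has a related mismatch. If the RR is constant, differs from 1, and baseline risk varies between strata, the stratum ORs cannot be equal. Breslow-Day therefore does not test the assumption under which a single common RR is a full summary. It also returns a P value with no estimate of how much the effect varies.

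**Working it through.** **Inputs.** Control SSI rate 10%, NPWT rate 7%, two-sided 5% test, 80% power, 5% loss (section 6.1.1, Table 4). Site SSI rates of 6% to 12% in all women (section 6.1.1). Composite adverse events 16% v 12% (section 6.1.2). Control SSI rate of 27.9% in the external pilot randomized trial (Table 1). The strength of the covariates is not in the document and is assumed below.

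**1. The plan's own figure.** Per arm, n = [z₀.₉₇₅√(2p̄(1−p̄)) + z₀.₈₀√(p₁(1−p₁)+p₂(1−p₂))]² / (p₁−p₂)², with p̄ = 0.085:
(1.960·√0.15555 + 0.842·√0.1551)² / 0.0009 = 1355.4, so 1356 per arm and 2712 in total. Allowing for 5% loss gives 2712/0.95 = 2855 or 2712 × 1.05 = 2848. The stated 2850 reproduces, and nothing below changes it.

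**2. Scale alone.** OR = [p₁/(1−p₁)] / [p₀/(1−p₀)].
- SSI 7% v 10%: RR = 0.700; OR = (0.07/0.93)/(0.10/0.90) = 0.677. A 30% reduction reads as 32%.
- Adverse events 16% v 12%: RR = 1.333; OR = (0.16/0.84)/(0.12/0.88) = 1.397.
- RR 0.70 at a 27.9% control rate: OR = (0.1953/0.8047)/(0.279/0.721) = 0.627.

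**3. Scale plus conditioning.** Let the prognostic score be normal with SD s on the logit scale. For each arm, solve for the intercept a such that the mean of expit(a + sZ), with Z standard normal, equals that arm's marginal risk. The conditional OR is exp(a₁ − a₀).

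| Assumed s | Approx. c-statistic | Conditional OR, SSI 7% v 10% | Conditional OR, adverse events 16% v 12% |
|---|---|---|---|
| 0.5 | 0.64 | 0.672 | 1.41 |
| 1.0 | 0.75 | 0.654 | 1.46 |
| 1.5 | 0.83 | 0.624 | 1.53 |

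In every SSI row the arms are balanced and the marginal RR is exactly 0.70. Read as a relative reduction, the adjusted result would be 33% to 38% instead of 30%.

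**4. The same model can return the RR.** With s = 1 the intercepts are −2.564 (standard care) and −2.989 (NPWT). Their difference gives exp(−0.4245) = 0.654. Averaging the predicted risks over the score gives back 10% and 7%, so RR = 0.07/0.10 = 0.70 and the risk difference is −3 percentage points.

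**5. Breslow-Day for SSI.** If the RR is 0.70 in two strata with baselines of 6% and 12%, the ORs are (0.042/0.958)/(0.06/0.94) = 0.687 and (0.084/0.916)/(0.12/0.88) = 0.672. Results of 20,000 simulated trials per scenario, with two strata of about 712 per arm, against an inverse-variance test of equal log RRs:

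| Scenario | Breslow-Day rejects | RR-scale test rejects | Tests disagree |
|---|---|---|---|
| RR 0.70 in both, baselines 6% and 12% | 5.3% | 5.1% | 0.7% |
| RR 0.70 in both, baselines 5% and 20% (assumed) | 5.5% | 4.9% | 2.1% |
| RRs 0.5 and 0.9 (assumed), baselines 6% and 12% | 47.9% | 50.1% | 2.2% |

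For SSI the two tests behave almost alike.

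**The case against.** The strongest reply is that section 6.2.2 is silent about scale; it does not choose the wrong one. It speaks of the probability of SSI and never of an odds ratio, its key sentence is about prognostic factors and not expressly about treatment, and a logistic model can deliver an adjusted RR by standardization. This stands in part: the model need not be replaced. But the paragraph promises adjusted treatment estimates, names no other method, and includes no step back to the RR.

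The size is also modest. With 1425 per arm and an observed RR of 0.70, SE(log RR) = √(1/99.75 + 1/142.5 − 2/1425) = 0.125, so the 95% CI is about 0.55 to 0.89. The gap between 0.70 and 0.677 is small against that. The larger conditional ORs need strong covariates; at s = 0.5, conditioning moves the OR only from 0.677 to 0.672. All of this stands.

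Pairing Breslow-Day with a Mantel-Haenszel analysis is conventional, and homogeneity always depends on scale. That also stands as a defence against calling the test invalid, but not against asking that the scale match the reported measure.

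Two stronger readings are tempting. A reader might infer that subgroup effects will be reported as odds ratios. The document does not say so: Breslow-Day is a test and estimates nothing, and the only measure named is the RR. A reader might also infer a contrast between an adjusted OR and an unadjusted primary RR. Section 6.2.1 plans a common RR beside a Cochran-Mantel-Haenszel test, which points to a stratified estimate (its strata are not named), so the primary result should not be called unadjusted.

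**Conclusion.** The mismatch is real and minor. As written, the default adjusted treatment estimate is a conditional OR that is not the same quantity as the trial's common RR. For SSI at 10% v 7%, it would be about 0.67 to 0.62 against an RR of 0.70, depending on an assumed prognostic-score SD of 0.5 to 1.5 for which the document gives no value. For adverse events at 16% v 12%, RR 1.33 becomes OR 1.40 before conditioning and 1.41 to 1.53 after it, on the same assumption. The homogeneity test has a null other than equal RRs, with negligible consequence for SSI at the site rates the plan quotes. The gap between RR and OR widens for more common outcomes. A reader might go further and doubt the main result, but the documents give no ground for that: the primary test, the primary RR and the sample size of 2850 do not depend on either method. Only secondary analyses are touched.

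**What to change.** Make two changes to the analysis plan before outcomes are compared by arm.

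- **Adjusted estimates (section 6.2.2).** Keep the logistic model. For each woman, predict risk under NPWT and under standard care, average each set over all women, and report the ratio and difference of the two averages with 95% CIs by the delta method or bootstrap. Modified Poisson regression with robust standard errors is an acceptable alternative for the RR. The standardized risk difference also suits the cost per SSI prevented, which uses the difference in SSI rates.
- **Subgroups (section 6.2.1).** Replace Breslow-Day with treatment-by-subgroup terms in a log-link (modified Poisson, robust SE) model that includes the randomization strata of section 4.4: site, BMI category and scheduled or unscheduled cesarean. Report the ratio of RRs with its 95% CI for each factor.

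If the team prefers the odds scale, the least it should do is say so and label the results as odds ratios.

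The cost is a few sentences of plan text and a few lines of code, with no new data and no change in sample size. The downside is slightly more analysis work and adjusted effects that look a little smaller than the corresponding odds ratios.

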#### *Cost-Effectiveness Analysis*

The economic analysis will be led by [name], MPP, MPH, PhD, an MFM Specialist and Health Economist with extensive experience in cost-effectiveness analysis. We will adhere closely to the guidelines for economic analysis accompanying clinical trials set forth by the international Task Force on Good Research Practices on RCT Cost-Effectiveness Analysis. The primary perspective of this economic evaluation will be societal, but we will also examine the patient and health care payer perspectives. This analysis will follow the intention-to-treat principle. The time horizon for the analysis will be the 30-day follow-up period of the trial, but we will include costs for treatment of SSIs beyond 30 days. Costs and effects will not be discounted because the time horizon for the analysis is short.

**Costs:** Direct medical costs will be the primary measure, but indirect costs may be considered if feasible. Direct medical costs will include the cost of implementing prophylactic NPWT or standard dressing (e.g., device or dressing cost, treatment of side effects), and medical care for SSI (e.g., hospital costs, emergency room, outpatient services, wound care supplies, and medications). Indirect costs will include cost of traveling for outpatient visits and lost productivity from being absent from work or usual activity. Secondary data sources will be used as much as possible to reduce the burden of data collection for economic analysis. Unit costs for inpatient and outpatient services, outpatient procedures, laboratory tests, and office visits will be estimated by using charges adjusted for cost-to-charge ratios. The unit cost of medications will be derived from average wholesale prices. Unit costs for study patients' time will be based on the average national wage rate.

**Effectiveness:** The effectiveness measures will be rate of SSI and QALYs. We will calculate QALYs by applying utility weights (1=perfect health, 0=death) to various health states values derived from the EuroQol five dimensions questionnaire (**EQ-5D**). The EQ-5D is a standardized instrument for measuring generic health status. The health status measured with EQ-5D-3L is used for estimating preference weight for that health status, then by combining the weight with time, QALYs can be computed. We will administer the EQ-5D to patients at the 30-day follow-up phone call. Once the data have been collected a scoring function can be used to assign a value (i.e., EQ-5D™ index score) to self-reported health states from a set of U.S.-generated value set (preference weights).

EQ-5D is one of the most commonly used generic health status measurement, and its good validity and reliability have been reported in various health conditions. The EQ-5D-3L questionnaire is made up for two components; health state description and evaluation. In the description part, health status is measured in terms of five dimensions (5D); *mobility, self-care, usual activities, pain/discomfort, and anxiety/depression*. Mobility dimension asks about the person's walking ability. Self-care dimension asks about the ability to wash or dress by oneself, and usual activities dimension measures performance in "work, study, housework, family or leisure activities". In the pain/discomfort

dimension, it asks how much pain or discomfort they have, and in the anxiety/depression dimension, it asks how anxious or depressed they are. The respondents self-rate their level of severity for each dimension using a three-level (3L) scale: *having no problems, having some or moderate problems, being unable to do/having extreme problems*. In the evaluation part, the respondents evaluate their overall health status using the visual analogue scale (EQ-VAS) which ranges from 0 (the worst health you can imagine) to 100 (the best imaginable health state).

**Cost-effectiveness:** The measures of cost-effectiveness of prophylactic NPWT will be incremental cost per case of SSI prevented and incremental cost per QALY. They will be calculated as follows.

Incremental cost per case of SSI prevented:

$(\text{Mean Cost}_{\text{Prophylactic NPWT}} - \text{Mean Cost}_{\text{standard care}}) \div (\text{Mean SSI Rate}_{\text{Prophylactic NPWT}} - \text{Mean SSI Rate}_{\text{standard care}})$

Incremental cost per QALY:

$(\text{Mean Cost}_{\text{Prophylactic NPWT}} - \text{Mean Cost}_{\text{standard care}}) \div (\text{Mean QALY}_{\text{Prophylactic NPWT}} - \text{Mean QALY}_{\text{standard care}})$

All estimates of costs, outcomes, and cost-effectiveness will be reported as means with 95% confidence intervals. In accordance with the current threshold used in the U.S., prophylactic NPWT will be considered cost-effective if the incremental cost per QALY is less than \$100,000^62. We will conduct sensitivity analysis to evaluate uncertainty of the results by varying probability (e.g., baseline rate of SSI, magnitude of risk reduction) and cost parameters (e.g., cost of the NPWT device, healthcare cost). We will employ Monte Carlo simulation to assess the robustness of our findings by simultaneously sampling distributions of multiple parameters within the model.

*Etiology, timing, and risk factors of SSIs in obese women*

For these analyses, the two study groups (NPWT and standard care) will be combined into a cohort, and all analyses will adjust for group assignment and study site. We will evaluate wound culture data to determine the types and frequency of different bacteria including MRSA. We will use time-to-event analyses to estimate median time to SSIs and time to heal. We will identify risk factors

for SSI initially based on factors associated with SSI in bivariate analysis (at  $P<0.1$  threshold), biological plausibility, and factors reported in the literature. We will use backwards elimination to reduce the number of variables in the model. Variables that are significant will be retained as risk factors for SSIs in obese women. Fit for the final model will be assessed by using the Hosmer-Lemeshow goodness-of-fit test.

*Other planned secondary analysis*

- Effect of prophylactic negative pressure wound therapy on a composite of any wound complication
- Effect of prophylactic negative pressure wound therapy on rate and type of wound cultures
- Effect of prophylactic negative pressure wound therapy on healthcare resource utilization
- Association between levels of cefazolin in the subcutaneous layer before fascial incision and after fascial closure and risk of surgical site infection
- Risk of surgical site infection and other wound complications with different skin incision types
- Relationship between skin microbiome at the incision site and risk of surgical site infection
- Subcuticular suture type and risk of surgical site infection
- Timing of removal of standard dressing and surgical site infection

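### Treatment costs of surgical site infection run past the 30-day horizon with no stated matching QALYs, and the only timed EQ-5D-3L is at day 30

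*Combined protocol and SAP*

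**What the plan says.** All of this is in Section 6.2.2, Cost-Effectiveness Analysis, unless another section is named.

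- **Horizon.** "The time horizon for the analysis will be the 30-day follow-up period of the trial", and the same sentence continues: "but we will include costs for treatment of SSIs beyond 30 days". Effects appear only in the next sentence: "Costs and effects will not be discounted because the time horizon for the analysis is short". No sentence extends QALYs beyond day 30.
- **Utility measurement.** "We will administer the EQ-5D to patients at the 30-day follow-up phone call". Section 4.6 gives the same single time. Section 5.1 lists the form without a time. The Schedule of Events in Section 4.5 marks a follow-up survey at day 2-7 and at day 30 but does not name the EQ-5D, and Section 4.6 describes the early contact as covering adverse events, pain and satisfaction with the dressing.
- **QALY construction.** "We will calculate QALYs by applying utility weights (1=perfect health, 0=death) to various health states values". Of the EQ-5D-3L weight the plan says "then by combining the weight with time, QALYs can be computed". It names a U.S. value set, but gives no starting value, interpolation rule or duration of any health state.
- **Decision and uncertainty.** "prophylactic NPWT will be considered cost-effective if the incremental cost per QALY is less than" $100,000. The sensitivity analysis varies probability and cost parameters; utilities and durations are not mentioned. The Monte Carlo step is described as "simultaneously sampling distributions of multiple parameters within the model", with no model structure given.

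**The concern.** Two features of the plan bear on the same ratio.

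First, the numerator and denominator can cover different periods. An SSI counts if it occurs up to day 30 (Section 4.8.1), so a late one can bring its full treatment cost but only the part of its health loss that falls before day 30.

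Second, the health effects at issue are short, and one reading on about day 30 is a poor summary of them. A woman whose SSI has healed by the call can score as if she never had one. A woman whose SSI began a few days earlier may have her low score applied to the whole month. The device is worn for at most 7 days (Section 4.5, Postoperative care), so a skin effect that clears soon after removal is over about three weeks before the call.

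What is at stake is the cost-per-QALY part of Secondary Aim 2 and the judgment against the $100,000 threshold. The primary outcome and the safety comparison are untouched, and cost per SSI prevented does not use the EQ-5D.

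**Working it through.** The documents give no QALY figure to reproduce, so this is an illustration of size.

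**Inputs from the documents.** SSI rates of 10% and 7%, a difference of 0.03 (Section 6.1.1); composite adverse events of 16% with NPWT and 12% with standard dressing, a difference of 0.04 (Section 6.1.2); threshold $100,000 per QALY (Section 6.2.2); Prevena price $500 (Section 2.3); EQ-5D-3L taken on day 30.

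**Assumptions, not in the documents.** A utility decrement d of 0.1 to 0.3, and the episode dates below. Loss in QALYs = days × d / 365.

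**(a) SSI on days 7 to 28, healed before the call.**
- True loss: 21d/365 = 0.0058 to 0.0173 QALY. The day-30 score can show 0.
- Per randomized woman, if every prevented SSI were of this kind: 0.03 × 0.0058 to 0.0173 = 0.00017 to 0.00052 QALY, or about $17 to $52 at the threshold.

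**(b) SSI on days 20 to 50, active at the call.**
- Whole loss: 30d/365 = 0.0082 to 0.0247. Up to day 30: 10d/365 = 0.0027 to 0.0082. After day 30: 20d/365 = 0.0055 to 0.0164, two thirds of the whole.
- If QALYs stop at day 30 and costs do not, that two thirds is left out while its treatment cost stays in. Per randomized woman, if every prevented SSI were of this kind: 0.03 × 20d/365 × $100,000 = about $16 to $49.
- If the day-30 score is instead applied to all 30 days, the result is 30d/365, three times the loss within the horizon. It equals the whole-episode loss here only because this episode happens to last 30 days.

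**(c) Skin effect on days 0 to 7.**
- True loss: 7d/365 = 0.0019 to 0.0058. The day-30 score shows 0.
- If the whole adverse-event difference were of this kind: 0.04 × 7d/365 × $100,000 = about $8 to $23 per randomized woman. Missing it favours NPWT, whereas missing (a) counts against NPWT if NPWT prevents SSIs.

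**Scale of the denominator.** On a 0-to-1 scale, if each prevented SSI would have meant all 30 days at utility 0, the gain within the horizon is 0.03 × 30/365 = 0.0025 QALY, worth about $247. That is below the device price before any savings, so the verdict will depend heavily on SSI costs avoided, and these are the one component allowed to run past the horizon. The documents give no figure for those later costs, so that side cannot be sized.

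**Would a second EQ-5D-3L at the day 2-7 contact settle it?** Use linear area under the curve with a first reading on day 4.
- (a) is still read as 0.
- (b) gives 0.5 × (30 − 4)d = 13d against 10d, or 1.3 times the loss within the horizon (1.4 times with a day-2 reading, 1.15 times with a day-7 reading).
- (c), with the affected reading held back to day 0, gives (4 + 13)d = 17d against 7d. The error is 10d/365, larger than the 7d/365 now missed.

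Only (b) improves.

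**The case against.** The strongest reply is that a patient-level calculation may not be intended. The plan refers to various health states, to varying the baseline SSI rate and the risk reduction, and to parameters within a model. These fit a state-based calculation at least as well, and under it cases (a) to (c) need not arise. This stands: the three cases show what follows if each woman's own score is used, not what the plan certainly does. What remains on that reading is that no states, durations or weights are given.

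Second, Section 5.3 leaves the analysis plan to be finalized, Section 1.3 refers to a Manual of Operations and data forms, and Section 6.2.2 commits to guidelines for trial-based economic evaluation. A rule may exist there. The claim is therefore limited to this document.

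Third, the plan discloses the later SSI costs openly and never says that QALYs stop at day 30, and its planned analysis of time to healing could supply durations. A reader might infer that truncation of effects is a stated decision. It is an inference from a 30-day horizon with an extension stated for costs alone. That is still enough to let the two periods differ if the plan is followed as written.

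Fourth, the amounts are small, and pain common to both arms cancels in the difference. This too stands, although the ratio can move more than the dollar figures suggest because its denominator is so small.

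**Conclusion.** As written, incremental cost per QALY can combine SSI costs that run past day 30 with effects confined to 30 days. If individual day-30 scores are used, it can also miss losses that resolve before the call and over-weight those present at it. This is more than missing detail, because the costs are explicitly extended and the effects are not.

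The size is modest: about $17 to $52 per randomized woman for missed resolved SSIs, resting on assumed decrements of 0.1 to 0.3, an SSI on days 7 to 28, and the planned 3-point difference in SSI.

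A reader might infer that the cost-effectiveness conclusion is biased in a known direction or would be reversed. The documents do not support that. The components pull in opposite directions, the net direction is unknown, and at these values the judgment would change only if the result lay within tens of dollars per woman of the threshold. Cost per SSI prevented is not affected.

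**What to change.** 1. **Match the periods.** For cost per QALY, make costs and QALYs cover the same time and report two versions: both ending at day 30, and both running to the end of the SSI episode as far as dates allow. Neither needs to be imposed as the only base case. Cost per SSI prevented may keep full episode costs.
2. **State how QALYs are built.** Apply a prespecified, sourced utility decrement for SSI, and one for device-related adverse events, over recorded episode dates, rather than relying on the day-30 score alone. Vary decrement and duration in the Monte Carlo analysis, and state a rule against double counting where the day-30 score falls inside an episode. If a state-based model is intended, write down its states, durations and the source of its weights.

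An EQ-5D-3L at the existing discharge/day 2-7 contact is an optional supplement for early utility, a few minutes per woman. It does not replace step 2.

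**Cost.** Mainly analysis-plan wording and analysis time. Episode start and healing dates are needed. The Schedule of Events names no healing-date item, and the last planned chart abstraction is at 4-6 weeks postpartum (days 28 to 42), so an SSI healing on day 50 would end at least 8 days after it and some dates may be incomplete. The decrements are external assumptions, which is why they need a stated source and a range.
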